The ICU staff (the physician or the nursing staff caring for the patient, or the research coordinator) will telephone the transfusion service to: 1) order the RBC units, 2) inform them of the patient's study inclusion and unique study identification number. The hospital transfusion service will be given the randomisation schedule for their site and the allocated study number will be identified on the schedule and the appropriate group (freshest or standard care) will be allocated to the patient.

For the freshest blood group, the transfusion service scientist will take the required number of compatible RBC units from the area of the fridge containing the freshest blood. For the standard care group, the transfusion service scientist will select the RBC units in accordance with the current practice and will take the required number of compatible RBC units from the area of the fridge containing the oldest blood.

The blood scientist will flag the patient's allocation in the transfusion service computer system to ensure they remain in the same study group throughout their primary hospital admission. In addition to this measure, while the patient is in ICU clinical staff will remind the transfusion service of the patient's study enrolment when ordering RBC. For any subsequent transfusion episodes in the operating theatre or on the ward, the blood scientists will be reminded by the computer flag.

At the time of the patient's primary hospital discharge the ICU RC will notify the blood bank to remove the computer flag. Patients who are readmitted to hospital and receive further transfusion will receive standard issue RBC.

Blinding

Study group allocation will be concealed from the treating medical and nursing staff and the research coordinator.

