Randomised patients will be followed up to death or 180 days post-randomisation. Data collection will be restricted primarily to those variables necessary to define clinical patient characteristics including: baseline demographics, primary diagnoses, physiological parameters, diagnostic interventions, therapeutic interventions and documentation of deaths and other adverse events.

Patients and/or their legal surrogate will be asked to provide three possible points of contact (home and close family contact details) to the research staff prior to discharge. For patients discharged alive from ICU, follow-up will be restricted to information concerning duration of hospital stay and vital status at hospital discharge, 90 days and 180 days post randomisation. In addition, patients (or a proxy – generally a close family member) that are alive at 180 days after randomization will be interviewed by the site RC using a simple standardized structured telephone questionnaire to measure quality of life EQ5D [48].

Data variables collected

- Demographic data:
 - Identity (initials, study number, date of birth, gender, postcode)
 - Blood group: A, B, O, AB, Rhesus status (positive or negative)
 - Alloantibodies (if present)
 - Co-morbidities: heart disease including angina, myocardial infarction and previous CABG, immuno-compromised
 - Ethnicity (for patients enrolled in New Zealand only)
- Hospital data
 - Hospital admission and discharge dates
 - Hospital discharge destination
- ICU data
 - ICU admission and discharge dates
 - Acute Physiology and Chronic Health Evaluation III [APACHE III] score and risk of death at ICU admission
 - Acute Physiology and Chronic Health Evaluation III [APACHE III] diagnosis code at admission
 - Current “unstable or active” heart disease –(cardiac arrest, arrhythmia, cardiogenic shock, angina, acute myocardial infarction)

- Sequential Organ Failure Assessment [SOFA] score at randomisation and daily during ICU admission
- Haemoglobin at ICU admission
- Requirement of invasive mechanical ventilation at randomisation
- Duration of mechanical ventilation
- Requirement of renal replacement therapy at randomisation
- Duration of renal replacement therapy
- Requirement of catecholamines at randomisation
- Duration of catecholamine administration
- Blood stream infection (date and pathogen)
- Transfusion information
 - Haemoglobin pre transfusion episode
 - Date and time of each RBC unit transfused

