The baseline mortality of intensive care patients enrolled in trials will be high due to the critical illness that has necessitated their ICU admission. They will frequently develop life-threatening organ failure(s) unrelated to study interventions and despite optimal management. Therefore, consistent with the advice of Cook et al[56], events that are part of the natural history of the primary disease process or expected complications of critical illness will not be reported as serious adverse events in this trial. Additionally, events already defined and reported as study outcomes (total mortality, febrile non-haemolytic transfusion reactions, bacteraemia, need for mechanical ventilation or renal replacement therapy) will not be labelled and reported separately as adverse events or SAEs unless they are considered to be causally related to the study intervention or are otherwise of concern in the investigator’s judgement.

Reporting

SAEs will be recorded on separate case report forms. SAEs which occur from the time of commencement of study treatment to 90 days post randomisation will be reported to the coordinating centre (ANZIC-RC) by faxing the provided SAE form. SAEs should be reported to the ANZIC-RC within 24 hours of study staff becoming aware of the event. Minimum information to report will include:

- Patient initials and study number
- Nature of the event
- Commencement and cessation of the event
- An investigator’s opinion of the relationship between study involvement and the event (unrelated, possibly, probably or definitely related).
- Whether treatment was required for the event and what treatment was administered.

SAEs must be reported on the fax form. Follow up reporting may be required. The SAE reports will then be forwarded to all sites for reporting to their HRECs in accordance with local requirements.

Attention:

[name]

Transfuse Project Manager

Fax number for SAE Reporting: [name]

Telephone Numbers: [contact]

FUNDING

The TRANSFUSE RCT is funded by a project grant from the National Health and Medical Research Council (NHMRC#1020694) and by the Australian Red Cross Blood Service. The ANZIC-RC will supply infrastructure and administrative support.

PUBLICATION

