APPENDIX 1 – SCHEDULE OF EVENTS

Assessments / Procedures		ICU admission	Pre-1 st RBC transfusion	Daily ICU Admission	ICU Discharge	Hospital Discharge	Follow-up – 28 days post-randomisation	Follow-up – 90 days post-randomisation	Follow-up- 180 days post randomisation
Screening log		X							
Inclusion & Exclusion criteria			X						
Demographic data			X						
Primary diagnosis		X							
Comorbidities			X						
Physiological parameters		X	X						
APACHE III		X							
SOFA			X	X					
Patient's blood group (ABO, Rh)			X						
Randomisation			X						
RBC Transfusion (each unit)	Haemoglobin pre-transfusion		X	X					
	Time & date of transfusion			X		X			
	RBC blood group (ABO, Rh)			X		X			
	Pack number			X		X			
	Collection and expiry dates			X		X			
	Blinding status (units checked by non-bedside nurse)			X					

Assessments / Procedures	ICU admission	Pre-1 st RBC transfusion	Daily ICU Admission	ICU Discharge	Hospital Discharge	Follow-up – 28 days post-randomisation	Follow-up – 90 days post-randomisation	Follow-up- 180 days post randomisation
Adverse Events			X					
Serious Adverse Events			X					
Number of units (ml) FFP post-randomisation			X					
Number of units platelets post-randomisation			X					
Febrile non-haemolytic transfusion reaction			X					
Requirement for catecholamine		X	X					
Requirement for Invasive Ventilation		X	X					
Requirement for Renal Replacement Therapy (RRT)		X	X	X				
Blood stream infection (date(s), pathogen(s))			X					
Vital status & cause of death				X	X	X	X	X
EQ5D								X

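### SAEs are reportable to day 90, but their collection is scheduled only on ICU days, so non-fatal SAEs after ICU discharge may be under-reported while allocated blood is still being given

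*Combined protocol and SAP*

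**What the plan says.** Four parts of the protocol bear on this point.

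- **Safety, Reporting.** The window is wide: "SAEs which occur from the time of commencement of study treatment to 90 days post randomisation will be reported to the coordinating centre". The trigger is awareness: "SAEs should be reported to the ANZIC-RC within 24 hours of study staff becoming aware of the event".
- **Appendix 1, Schedule of Events.** The row "Serious Adverse Events" has a single mark, under "Daily ICU Admission". The adverse events row is the same.
- **Data Management, Data collection methods.** Once a patient leaves ICU alive, "follow-up will be restricted to information concerning duration of hospital stay and vital status at hospital discharge, 90 days and 180 days post randomisation". EQ5D is added at day 180 for survivors.
- **Study Procedures, Randomisation.** Allocation is flagged in the transfusion service computer "to ensure they remain in the same study group throughout their primary hospital admission". Blood given after ICU is included: "For any subsequent transfusion episodes in the operating theatre or on the ward, the blood scientists will be reminded by the computer flag".

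The section on the data safety committee names two between-arm comparisons for the one planned interim look, at 2500 of 5000 patients: all-cause mortality and cumulative SAE reports.

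**The concern.** The period for which SAEs are reportable, the period in which they are scheduled to be collected, and the period of randomised exposure are all different. Reportability runs to day 90. Scheduled collection ends with the ICU stay. Exposure ends at primary hospital discharge.

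Between ICU discharge and hospital discharge, a patient can receive allocated units, and the units are logged, but no scheduled item asks about non-fatal harm. Whether such an event reaches the coordinating centre depends on whether study staff, who are ICU-based, happen to hear of it. It also depends on how a site reads an instruction that restricts post-ICU follow-up alongside one that makes SAEs reportable to day 90.

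At stake is the reach of one of the two comparisons named for the monitoring committee. A non-fatal harm that arises mainly from transfusion after ICU would be less likely to show in the SAE counts.

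**Working it through.** The plan states no figure on this point, so the check sets the passages side by side.

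**1. Marks in Appendix 1.** The schedule has eight time columns: ICU admission, before the first transfusion, daily in ICU, ICU discharge, hospital discharge, and days 28, 90 and 180.

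| Row | Daily in ICU | ICU discharge | Hospital discharge | Day 28 | Day 90 | Day 180 |
|---|---|---|---|---|---|---|
| Adverse events | X | | | | | |
| Serious adverse events | X | | | | | |
| Febrile non-haemolytic reaction | X | | | | | |
| RBC unit: time and date, group, pack number, collection and expiry dates | X | | X | | | |
| Renal replacement therapy (also marked before first transfusion) | X | X | | | | |
| Vital status and cause of death | | X | X | X | X | X |

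The SAE row is marked in 1 of 8 columns and in 0 of the 5 columns that follow the ICU days. The positions were read from extracted text. The five vital-status marks fall exactly in the last five columns, which supports the alignment. Later columns are filled where later collection is meant, so the empty SAE cells are not just a feature of the layout.

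**2. The three periods.**

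- Reportable: start of study treatment to day 90.
- Scheduled SAE collection: ICU days.
- Allocated blood: until primary hospital discharge. Readmitted patients then receive standard issue.

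The interval that matters is ICU discharge to primary hospital discharge: exposure continues and is recorded, and SAEs are reportable, but nothing schedules their collection. From hospital discharge to day 90 SAEs remain reportable, again with no scheduled enquiry, but no further allocated blood is given.

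**3. What is still captured after ICU.** Deaths with cause are recorded to day 180. Any SAE that staff learn of by day 90 is reportable. Ongoing renal replacement therapy is asked at day 90, for the renal substudy (Appendix 4). What remains is non-fatal SAEs that nobody is scheduled to ask about.

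**4. Is ICU-only collection the intention?** The secondary outcomes say explicitly that febrile reactions and blood stream infection are counted in ICU. The SAE window carries no such limit. If ICU-only was meant, the Reporting section needs changing; if day 90 was meant, Appendix 1 and the data collection section do.

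**5. Effect on the committee's comparison.** Let c be the probability that a post-ICU SAE is reported, and suppose c is the same in both arms. The expected between-arm difference in reported post-ICU SAEs is then c times the true difference. With c below 1 the difference shrinks, and the cumulative total is weighted towards ICU events. The documents give no basis for a value of c, nor for the share of units or SAEs after ICU.

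**The case against.** The best defence is that SAE reporting is driven by events, not visits. The day-90 duty binds every site whatever Appendix 1 marks, and a schedule of assessments does not narrow it. The data collection section itself includes adverse events among the data to be gathered. Its restriction on post-ICU follow-up is not applied strictly elsewhere, since Appendix 1 also asks for unit data at hospital discharge and for cause of death. Gathering the unit data gives staff a chance to hear of a reaction.

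Much of this stands, and it rules out stronger readings that a reader might infer:

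- **That post-ICU toxicity is missed, or that no SAE is collected after ICU.** The documents do not support this. The awareness-based duty continues and fatal events are captured.
- **That all theatre transfusions are uncovered.** Theatre blood given during the ICU stay falls within daily ICU collection. The gap starts at ICU discharge.
- **That the gap can be sized in calendar days.** Appendix 4 gives 28 days as the length of trial follow-up in ICU, so one could count at least 90 - 28 = 62 days without scheduled SAE collection. Those days include time after hospital discharge with no randomised exposure, and days are not a share of SAEs.
- **That the committee would be shown a count labelled as 90-day.** No passage says so; the text refers only to cumulative reports.
- **That uneven reporting between sites biases the comparison.** Randomisation is stratified by centre, so site differences need not favour either arm. The likelier cost is lost sensitivity and an unclear scope.

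The committee also compares mortality and may request other trial data at any time. But it cannot request events that were never ascertained, and no passage schedules an enquiry that would bring a ward event to the study staff's attention.

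**Conclusion.** The point holds as an internal inconsistency with a modest consequence. Non-fatal SAEs after ICU discharge are reportable to day 90 but have no scheduled collection point, although allocated blood may still be given until primary hospital discharge. They may be under-reported, to a degree that varies between sites, and the monitoring committee's SAE comparison would then rest mainly on ICU events. Mortality and cause of death are unaffected.

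The size cannot be calculated, because the documents do not say what share of units or SAEs falls after ICU. The conclusion rests on the marks in Appendix 1 being read in the right columns, and on there being no post-ICU SAE enquiry in site materials outside these documents. It should be corrected because the remedy is cheap and bears on one of the two comparisons named for the only planned interim look.

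**What to change.** Reconcile the Reporting section, Appendix 1 and the data collection section in one of two ways.

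1. **If day 90 is intended:** add SAE marks in Appendix 1 at ICU discharge, hospital discharge and day 90, and add SAEs to the items collected after ICU discharge in the data collection section.
2. **If ICU-only collection is intended:** narrow the window in the Reporting section to match, and describe the committee's SAE comparison as covering ICU events only.

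The first option uses contacts that already exist. The coordinator acts at hospital discharge to have the allocation flag removed, a day-90 telephone follow-up is planned, and the renal substudy has already added a question to it. The cost is amendment wording, a few case report form fields, one question at each contact, and a little more reporting by sites. The second option needs only wording, but accepts that non-fatal harm after ICU lies outside the SAE comparison.

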APPENDIX 1 – SCHEDULE OF EVENTS

Assessments / Procedures		ICU admission	Pre-1 st RBC transfusion	Daily ICU Admission	ICU Discharge	Hospital Discharge	Follow-up – 28 days post-randomisation	Follow-up – 90 days post-randomisation	Follow-up- 180 days post randomisation
Screening log		X							
Inclusion & Exclusion criteria			X						
Demographic data			X						
Primary diagnosis		X							
Comorbidities			X						
Physiological parameters		X	X						
APACHE III		X							
SOFA			X	X					
Patient's blood group (ABO, Rh)			X						
Randomisation			X						
RBC Transfusion (each unit)	Haemoglobin pre-transfusion		X	X					
	Time & date of transfusion			X		X			
	RBC blood group (ABO, Rh)			X		X			
	Pack number			X		X			
	Collection and expiry dates			X		X			
	Blinding status (units checked by non-bedside nurse)			X					

Assessments / Procedures	ICU admission	Pre-1 st RBC transfusion	Daily ICU Admission	ICU Discharge	Hospital Discharge	Follow-up – 28 days post-randomisation	Follow-up – 90 days post-randomisation	Follow-up- 180 days post randomisation
Adverse Events			X					
Serious Adverse Events			X					
Number of units (ml) FFP post-randomisation			X					
Number of units platelets post-randomisation			X					
Febrile non-haemolytic transfusion reaction			X					
Requirement for catecholamine		X	X					
Requirement for Invasive Ventilation		X	X					
Requirement for Renal Replacement Therapy (RRT)		X	X	X				
Blood stream infection (date(s), pathogen(s))			X					
Vital status & cause of death				X	X	X	X	X
EQ5D								X

APPENDIX 2 – EURO QUALITY OF LIFE (EQ 5D)

By placing a cross in one box in each group below please indicate which statement best describes your own health state today

- Mobility

- I have no problems in walking around
 - I have some problems in walking around
 - I am confined to bed
-
-

- Personal care

- I have no problems with personal care
 - I have some problems with personal care
 - I am unable to wash or dress myself
-

- Usual activities(eg: work, study, housework, leisure activities)

- I have no problems with performing my usual activities
 - I have some problems with performing my usual activities
 - I am unable to perform my usual activities
-

- Pain/discomfort

- I have no pain or discomfort
 - I have some pain or discomfort
 - I have extreme pain or discomfort
-

- Anxiety/depression

- I am not anxious or depressed
 - I am moderately anxious or depressed
 - I am extremely anxious or depressed
-

APPENDIX 3 – THE IRON TRANSFUSE SUB STUDY (THE IT STUDY)

Investigators (in alphabetical order)

[name], [name], [name], [name], [name], [name], [name] and A/[name] on behalf of the TRANSFUSE investigators.

Aims:

To investigate changes in iron metabolism, bacterial growth in plasma and inflammatory profile after red blood cell (RBC) transfusion, and the role played by the duration of RBC storage in these changes, in critically ill patients.

Background:

Age of blood, iron metabolism and the TRANSFUSE trial

One third of patients hospitalised in intensive care unit (ICU) will be administered an average of 3 to 4 RBC units during their ICU stay [1, 2]. While RBC transfusion is considered lifesaving, their administration is independently and significantly associated with an increase in mortality and morbidity in this population [7]. Mechanisms for this potential harmful effect are not understood, however experimental studies suggest that blood storage duration may play a key role through RBC storage lesions, including accumulation of bioactive substances over the storage period.

One of the main consequences of the RBC storage lesion is the increase in extra vascular haemolysis in both the RBC unit and recipient, which results in a large amount of iron delivered to the recipient. Studies in animals, healthy volunteers and non-critically ill patients have described that transfusion of older RBC, compared to fresher RBC, leads to an increase in extra vascular haemolysis, an increase in non-transferrin bound iron (NTBI) and to a pro-inflammatory cytokine storm within the first hours after transfusion [57, 58]. NTBI is also involved in oxidative damage [59] [60], expression of endothelial adhesion molecules [61] and bacterial growth [62] [60]. For instance, it was reported, in 33 preterm infants, that transfusion of older RBC units was associated with a significantly higher concentration of malondialdehyde (MDA) 4 hours after transfusion compared to fresh RBC [59], suggesting elevated oxidative stress. However, these studies are restricted to animals or a non ICU-adult population and are limited in their sample size and design. Underlying disease appears to be a determinant in the occurrence of post transfusion adverse events [63].

A large prospective study on pathophysiological consequences of RBC transfusion and RBC storage duration in critically ill patients is required to: i) better understand how old RBC may promote inflammation, bacterial growth, oxidative damage and leucocyte adhesion, and ii) to define the patients most at risk of these adverse effects.

The TRANSFUSE (sTandaRd Issue TrANsfusion versus Fresher red blood cell Use in intenSive carE)-trial (ACTRN12612000453886) enrolls heterogeneous critically ill patients who did not receive blood before intensive care unit (ICU) admission and aims to determine whether freshest available allogeneic RBC compared to standard practice is associated with a decrease in mortality. This randomised controlled trial (RCT), conducted in Australia, New-Zealand and Europe, is the largest ongoing RCT on age of blood in critically ill patients at this time.

The TRANSFUSE-trial provides a unique opportunity to study how the RBC storage lesion may be harmful in critically ill patients. This study will provide valuable data on in vivo iron metabolism after RBC transfusion and other pathophysiological consequences of RBC storage lesions. These include: i) changes in bacterial growth in plasma before and after transfusion and between patients who received old and fresh RBC post-transfusion; ii) inflammatory profile post-RBC transfusion in patients receiving fresh vs. old RBC, and iii) plasma induced changes to leukocyte-endothelial interaction and the difference in leucocyte adhesion in patients receiving fresh vs. old RBC.

Significance

The project aims to address important and unresolved questions regarding potential mechanisms for any adverse effect from the storage age of RBC on patient outcomes. These data will provide detailed measurements of the potential pathways (iron, inflammation, propensity to infection) by which RBCs may produce adverse outcomes in patients. Importantly, by utilising the randomised design of the TRANSFUSE trial, this study will be able to investigate the effect of age of RBCs on these potential pathways. Identification of this mechanism could help future researchers develop specific approaches to preventing these adverse effects. The findings of this project will contribute to the development of strategies to address these effects and inform clinical practice, both in the intensive care and other clinical settings. They will also form the basis for a future potential NHMRC project grant to fund further studies into the mechanisms of adverse effects of transfusion. The collection of patient samples while the TRANSFUSE-trial is recruiting will be an invaluable resource for further research on the mechanisms of adverse effects from RBC transfusion in critically ill patients.

Objectives*Hypothesis*

Transfusion of older RBC compared with freshest available RBC leads to greater extravascular haemolysis and subsequent increase in NTBI resulting in an increase in bacterial growth and inflammation.

Primary Outcome

Indices of increased erythrocyte damage (extravascular haemolysis, iron indices including NTBI and labile plasma iron [LPI]) at 4-hour and 24-hours post the first RBC.

Secondary Outcomes

Bacterial growth in plasma at 4-hour and 24-hours post the first RBC.

Inflammatory cytokines at 4-hour and 24-hours post the first RBC transfusion

Leucocyte adhesion at 4-hour and 24-hours post the first RBC transfusion

Study Design

A sub study of patients enrolled in the TRANSFUSE randomised control trial.

Recruiting Site

The Alfred Hospital Melbourne, the Austin Hospital Melbourne and Monash Medical Centre Melbourne

Inclusion criteria

- Patients randomised in the TRANSFUSE trial and who are going to receive their first RBC transfusion in the current admission in ICU

Exclusion Criteria

- Current therapy with iron supplementation or iron chelation.

Ethics and consent

Appropriate Human Research and Ethics Committee (HREC) approval and Research Governance, including the use of opt-out consent has been obtained for the TRANSFUSE trial at each participating site. Application for an amendment will be made to the HREC to approve the inclusion of this study. Prospective consent will be obtained from the patient or the person responsible in the first instance, and if this is not possible telephone consent will be sought. If no person responsible is contactable after reasonable attempts, patients will be enrolled under section 42T.

Researchers will ensure that the requirements for section 42T are met before proceeding –

- Patient will not regain capacity within a reasonable time
- The person responsible cannot be ascertained or contacted despite making reasonable efforts
- The medical research procedure is not contrary to the person's best interests
- The medical research procedure is not against the wishes of the person
- The HREC has agreed that the procedure may proceed for a person where that person or their person responsible is unable to consent
- The purpose of the research is to test the effectiveness of the proposed therapy
- The procedure poses no greater risk than the risk inherent in the person's condition and alternative treatment
- The researcher must tell the patient or their person responsible of the medical research procedure once the patient has regained capacity or the person responsible has been ascertained or located and that they are advised that they may withdraw from the treatment.

A copy of the section 42T form will be submitted to the HREC and also to the Office of the Public Advocate.

[figure not shown]
Patients and the person responsible (if applicable) will be given the plain language and information form including details about the study design, methodology and significance.

Research plan and Methods

One hundred and fifty patients will be included in this sub-study. Wherever possible eligible patients will be enrolled consecutively.

After randomisation in the TRANSFUSE-trial, a sample of 18 ml (3 1/2 teaspoons) of blood will be taken before the first RBC unit, at 4 and 24 hours after the transfusion episode.

Figure. Study procedures

Patient and transfusion data: will be routinely collected as part of the data collected for the TRANSFUSE-trial. Dates and times when samples are taken and results of the experiments performed in the study sites will be recorded in a separate case report form (CRF).

Blood samples: Blood samples (2 x5 ml in lithium heparin tube, 1 x K2E 3ml EDTA (lilac top) tube and 1 x 5 ml in gel lithium heparin) will be sent immediately to the pathology lab of each hospital where plasma samples will be aliquoted and stored at - 80°C before transfer to the Australian Red Cross Blood Service Melbourne Processing Centre (MPC), where they will be stored until recruitment is complete and experiments are performed. For further details refer to the section below “blood sample schedule.”

Experiments:

- Bilirubin, free haemoglobin, haptoglobin, ferritin, serum iron, transferrin and transferrin saturation will be performed in each pathology laboratory at the 3 participating centres.
- The other experiments will be performed at a later date once all patients have been enrolled and samples collected. These experiments are outlined below:
 - i) Non transferrin bound iron (NTBI) and labile plasma iron (LPI, a fraction of NTBI that is redox active) will be measured by FeROS eLPI and LPI assays (Aferrix, Israel), and serum hepcidin will be measured using a commercially available ELISA (DRG, Germany).
 - ii) Bacterial growth will be performed in plasma before and after transfusion without and with desferrioxamine as described elsewhere [64].
 - iii) Inflammatory biomarkers: sCD106 (VCAM-1), sCD62L, sCD62P, ICAM-1, MCP-1, MIP-1a, MIP-1 β , IL-1 α , IP-10, IL-6, IL-8, IL-10, IL-12, IL-4, IL-13, IL-17, IL-21, IFN- γ and IFN- α , will be assessed in plasma samples via multiplex Cytometric Bead Array (BD Biosciences).
 - iv) Leucocyte adhesion

Blood samples schedule

Samples will be taken within 1 hour prior to transfusion (T0), 4 hours after transfusion initiation (T4) and 24 hours after transfusion initiation. For example, if the first RBC transfusion starts at 10 am, the samples T0 will be taken between 9 am and 9.59 am, at 2 pm (samples T4) and at 10 am the following day (samples T24).

In pathology, samples will be processed by the pathology laboratory staff. Supernatant will be removed and 0.5ml of plasma will be aliquoted and stored in cryovials at -80 degrees Celsius. At least five tubes per patient for each collection time-point will be stored. They will include four cryovials of plasma with heparin and one cryovial of plasma with EDTA. The storage tubes will be pre-labelled with the study number, the date, time and type of collection tube used (i.e. EDTA or lithium heparin). Patient identifiers will not be used on the cryovials.

Each week, a research assistant ([name] student) from the Blood Service will collect the samples from the 3 sites and transfer them with ice to the MPC. The patient samples will be kept at -80 degrees Celsius until the study recruitment has been completed, when the samples will then be transferred for analysis.

		Samples/volume collected	Processing and storage	Tests
T0 Sample	Before transfusion of the first RBC unit	1x5ml lithium heparin tube	Processed in laboratory for immediate analysis as per laboratory protocol	Iron studies: ferritin, transferrin, transferrin saturation, serum iron Haptoglobin
		1 x5ml gel lithium heparin tube	Processed in laboratory for immediate analysis as per laboratory protocol	Free haemoglobin
		1 x5ml lithium heparin	^Centrifuge and aliquot for -80 degrees Celsius storage into: Plasma in heparin, (5	Non-transferrin bound iron Labile plasma iron Hepcidin

			tubes of 0.5ml)	Bacterial growth
		1 x3ml EDTA tube	^Centrifuge and aliquot for -80 degrees Celsius storage into: Plasma in EDTA, (2 tubes of 0.5ml)	Inflammatory biomarkers (as listed above)
T4 Sample	4 hours after transfusion initiation*	1x5ml lithium heparin tube	Processed in laboratory for immediate analysis as per laboratory protocol	Iron studies: ferritin, transferrin, transferrin saturation, serum iron Haptoglobin
		1 x5ml gel lithium heparin tube	Processed in laboratory for immediate analysis as per laboratory protocol	Free haemoglobin
		1 x5ml lithium heparin	^Centrifuge and aliquot for -80 degrees Celsius storage into: Plasma in heparin, (5 tubes of 0.5ml)	Non-transferrin bound iron Labile plasma iron Hepcidin Bacterial growth
		1 x3ml EDTA tube	^Centrifuge and aliquot for -80 degrees Celsius storage into: Plasma in EDTA, (2 tubes of 0.5ml)	Inflammatory biomarkers (as listed above)
T24 Sample	24 hours after transfusion initiation*	1x5ml lithium heparin tube	Processed in laboratory for immediate analysis as per laboratory protocol	Iron studies: ferritin, transferrin, transferrin saturation, serum iron Haptoglobin
		1 x5ml gel lithium heparin tube	Processed in laboratory for immediate analysis as per laboratory protocol	Free haemoglobin
		1 x5ml lithium heparin	^Centrifuge and aliquot for -80 degrees Celsius storage into: Plasma in heparin, (5 tubes of 0.5ml)	Non-transferrin bound iron Labile plasma iron Hepcidin Bacterial growth
		1 x3ml EDTA tube	^Centrifuge and aliquot for -80 degrees Celsius storage into: Plasma in EDTA, (2 tubes of 0.5ml)	Inflammatory biomarkers (as listed above)

*In the event that multiple RBC units are transfused in the transfusion episode, samples will still be taken 4 hours after initiation of the first RBC transfusion

^Centrifugation will be performed at 16 degrees for 10 minutes with a speed of 2898 G

Data analysis and statistics

Sample size: 150 patients. Enrolment of 150 patients will enable detection of a difference in NTBI at 4 hours of 2.2uM with SD of 3.7 (similar to that shown in healthy volunteers in the study by Hod et al., Blood 2011 [62]),

between patients receiving fresh and older RBC units, accounting for a 20% incomplete data collection rate (which is expected due to the complex management requirements of patients enrolled in this study). Recruitment of 150 patients prior to the completion of the TRANSFUSE-trial (anticipated 18-months from commencement of the sub-study) is feasible based on the 3 centre's current combined recruitment rate of approximately 8 patients per month within usual working hours.

Statistical analysis: Data collected for the sub-study will be treated and analysed separately after the TRANSFUSE RCT has been completed. Data will be transformed when skewed and analysis performed on log-transformed values. Parameters before and after the transfusion episode will be compared for each patient using paired t-test. Biological parameters post-transfusion, as well as differences between pre- and post-transfusion values, will be compared according to RBC storage duration category, which will be defined according to the RCT (i.e.: freshest available vs. standard issue) and also according to whether patients were transfused with only RBC younger than 14 days vs. patients transfused with RBC older than 14 days. A correlation between patient severity at randomisation and each parameter (including: post-transfusion extravascular haemolysis and NTBI) will also be performed. A sub group analysis will be performed on the most severe patients according to their SOFA score on the day of transfusion.

Safety

As per the TRANSFUSE trial. There are no additional risks posed by the IT TRANSFUSE sub-study. The results of the study will be forwarded to the Data and Safety Monitoring Committee (DSMC).

Funding

This study is collaboration with the Australian Red Cross Blood Service, who has provided funding for the costs for research staff time, sample collection, processing and testing in addition to in kind support provided by the Blood Service.

Publication

The study will be conducted in the name of Monash University on behalf of the TRANSFUSE investigators. Authorship will be under the names of the sub-study investigators on behalf of the TRANSFUSE investigators. Publication of results will be embargoed until publication of the main study results unless specific permission for early publication is given by the TRANSFUSE management committee.

